Medically assessed, RSV-associated hospitalizations (Birth to 365 days post-birth)	O ⁴	O ⁴	O ⁴	O ⁴	O ⁴	O ⁴	O ⁴	O ⁴	O ⁴	●	Sections 8.3.1, 8.3.3, 8.4 and 10.3.8.
SAEs, (S)AEs leading to study withdrawal, MAEs (Birth to 365 days post-birth)	●	O	●	●	●	●	●	●	●	●	Sections 7.2, 8.3.1 and 10.3.8
Symptom-directed physical examination (includes RTI signs, symptoms)										●	Section 8.4.4
Nasal swab										●	Sections 8.1.1 and 8.4.4.2
Study conclusion								●			Sections 4.4 and 10.1.9

LAR = legally acceptable representative; V= visit; C = contact; D=day; NB = newborn.

● indicates a study procedure that requires documentation in the individual eCRF.

○ indicates a study procedure that does not require documentation in the individual eCRF.

CONFIDENTIAL

214725 (RSV MAT-012)
Protocol Amendment 1 Final

¹ Record at Visit 1-NB and if changes in lifestyle characteristics thereafter.

² Adjust volume if weight \leq 2.5 Kg. If no cord blood was collected, an infant blood sample must be collected within 72 hours after birth.

³ One sample at one of these visits, as per infant's assigned sub-cohort. Adjust volume if weight \leq 2.5 Kg.

⁴ RTI unscheduled visit should be planned in case the infant participant has any symptoms or signs as defined in Section 8.4.3.2.

⁵ ***An additional recommended safety contact may be performed ~7 days post-birth if deemed necessary by the investigator or by the parent/ LAR(s).***

⁶ ***Due to the change in the study requirements, there will no longer be collection of blood samples at Visit 2-NB, Visit 3-NB and Visit 4-NB.***

In times of special circumstances, refer to Section 8 for study procedures.

Note:

Contact may be via telephone, SMS, email, video-telephone/telemedicine or other means, depending on local best practice. If the study site is the participant's primary healthcare facility, contact with study personnel may also be made in the context of a visit for routine or event-driven care.

The timing of an event-driven visit cannot be defined with precision in the protocol.

Table 3 Allowed windows for study visits (Amended 15 March 2022)

Visit	Study Day ^a	Allowed visit window ^b
Maternal participants		
Screening	Up to 28 days prior to Visit 1	Day (-28) - Day 1
Visit 1	Day 1	Day 1
Contact 1	Day 8	Day 8 – Day 12
Visit 2 ^c	Day 31	Day 21 – Day 46
Monthly contacts until delivery	every 30 days	every 25 – 35 days
Visit 3 (Delivery) ^d	-	1 day before to 3 days after delivery^e

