6.8.1. Maternal participants (Amended 15 March 2022)

- **All folate and iron supplements** beginning the month before the estimated date of conception and continuing through delivery (i.e., through Visit 3). These supplements should be reported when taken independently and/or when included in a multivitamin mineral supplement.
- **All antibiotics, antivirals, analgesics, and anti-pyretics** taken within 7 days before dose administration.
- **All concomitant vaccines** beginning the month before the estimated date of conception and throughout the study (i.e., through Contact 2).
- **Prophylactic medication** related to the effects (actual or anticipated) of study vaccine/product administration (e.g., medication administered either in the absence of ANY symptom and in anticipation of a reaction to the study vaccine, or to prevent re-occurrence of one or more post-study intervention AEs such as headache).
- Any concomitant **medications/products** given for pre-existing medical conditions, beginning at Visit 1 and ending at Contact 2 (Day 1 to Day 181).

- Any concomitant **medications/products** associated with a solicited event or with an unsolicited AE, beginning at Visit 1 and ending at Visit 2 (Day 1 to Day 31).
- Any **corticosteroids for fetal lung maturation** administered prior to/during labor or delivery, as well as any **antibiotics** administered in the last week prior to delivery and/or during labor. Note: Standard of care medications/products administered routinely during labor/delivery (eg. general/regional/local anesthetics, analgesics, etc) do not need to be reported.
- Any concomitant **medications/products** associated with a MAE other than an MA-RTI beginning at Visit 1 and ending at Visit 4 (Day 1 to Day 43 post-delivery).
- Any concomitant **medications/products** associated with an MA-RTI beginning at Visit 1 and ending at Contact 2 (Day 1 to Day 181 post-delivery).

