9.3.1. Criteria for elimination from analysis

The Statistical Analysis Plan (SAP) will provide a complete list of criteria for elimination from the analysis sets. Criteria may include, but are not limited to, those in Sections [9.3.1.1](#) and [9.3.1.2](#).

9.3.1.1. Intercurrent medical conditions and concomitant medications / products / vaccines that may lead to elimination of a participant (maternal/infant) from per protocol analyses (immunogenicity)**9.3.1.1.1. Maternal participants**

- Any of the medications listed in Section [5.2.1.2](#) if administered up to delivery (Visit 3).

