The RSVPreF3 IgG ELISAs will be based on an indirect ELISA allowing the detection and the quantification of specific IgG antibodies directed against RSVPreF3 in human serum samples.

The principle of these assays will be as follows. RSVPreF3 antigen will be adsorbed onto a 96-well polystyrene microplate. After a washing and a blocking step, dilutions of serum samples, controls and standards will be added to the coated microplate. A reference standard curve will be prepared using a pool of commercial human serum containing anti-RSV antibodies. After incubation, the microplate will be washed to remove unbound primary antibodies. Bound IgG will be detected by the addition of a secondary anti-human antibody (total IgG or IgG1-specific), conjugated to HRP. Bound antibodies are quantified by the addition of the HRP substrate, tetramethylbenzidine and hydrogen peroxide, whereby a colored product develops proportionally to the amount of anti-RSVPreF3 IgG or IgG1 antibodies present in the serum sample. The optical density of each sample dilution is then interpolated on the reference standard. The corresponding antibody concentration, corrected for the dilution factor, is expressed in arbitrary ELISA Laboratory Units per milliliter (ELU/mL).

Hematocrit assay

The hematocrit is the proportion of the volume occupied by the red blood cells compared to the whole volume of the blood cells. The hematocrit value is determined by drawing blood sample into a capillary tube then centrifuged, the lengths of the columns for the red blood cells and the whole blood cells are measured using a graphic reading device. Thereafter, the proportion of the red blood cells to that of the whole blood cells is determined and expressed as a decimal or percentage fraction.

Hematocrit will be tested at Visits 1, 2 and 3 for all participants until the current Protocol Amendment 1 is approved (unless IEC/IRB allows for immediate implementation of this measure to reduce participant's burden, prior to full Amendment 1 being approved) in the respective study country(ies). Testing will be performed by a central laboratory. Results will be used to help evaluate changes over time in antibody titers / concentrations that may be related to volumetric changes during pregnancy, if deemed necessary.

10.3. Appendix 3: Adverse Events: definitions and procedures for recording, evaluating, follow-up, and reporting Definition of AE

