2090.Vx	Subjects did not comply with blood sample schedule: 
 • For PPS at Day 31, check the interval from vaccination to day 31 BS = 20 – 45 days; • For PPS at Delivery, check the interval from delivery to delivery BS = 1 day before to 3 days after delivery; 	Visit 2/Day 31, Visit 3/Delivery	Immunogenicity
2100.Vx	Serological results not available post-vaccination	Visit 2/Day 31, Visit 3/Delivery	Immunogenicity
2120.Vx	Obvious incoherence or abnormality or error in data	Visit 2/Day 31, Visit 3/Delivery	Immunogenicity
2130.Vx	Testing performed on samples not aligned with ICF	Visit 2/Day 31, Visit 3/Delivery	Immunogenicity

*Attribution of these elimination codes to subject need CRDL review of individual listing

** Attribution of code 1070 to a subject requires CRDL confirmation

Vx+ indicates subjects whose immunogenicity data will be eliminated from a specific visit onwards; Vx indicates subjects whose immunogenicity data will be eliminated from a specific visit.

DOB-Date of Birth, VAC-Vaccination, BS- Blood Sample

BS- Blood Sample.

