3.2.3.2. Excluded participants from Per-protocol analysis set of infant participants

An infant participant will be excluded from the PPS analysis under the following conditions.

Table 8 Elimination code and condition for infant participants

Code	Condition under which the code is used	Visit (timepoints) where the code is applicable	Applicable for analysis set/endpoint
800	Fraudulent data	All	All
900	Invalid informed consent - infant	All	All
901#	Invalid informed consent - mother	All	All
1030#	Study vaccine not administered at all	All	Safety, immunogenicity
1040.Vx+*	Administration of concomitant vaccine(s) forbidden in the protocol - infant	Visit 2-NB/Day 43 post-birth Visit3-NB/Day 121 post-birth Visit4-NB/Day 181 post-birth	Immunogenicity
1041#*	Maternal administration of concomitant vaccine(s) forbidden in the protocol up to Delivery	All	Immunogenicity
1050#	Maternal randomisation failure	All	Immunogenicity
1060#	Maternal randomisation code was broken	All	Immunogenicity
1070#	Maternal participants got vaccinated with the correct vaccine but containing an incorrect volume	All	Immunogenicity
1070#	Vaccination not according to protocol (site of injection, route of administration, wrong replacement of study treatment administered)	All	Immunogenicity
1070#	Study treatment not prepared as per protocol (e.g. reconstitution)	All	Immunogenicity
1070#	Other deviations related to wrong study treatment/administration/dose	All	Immunogenicity

CONFIDENTIAL

Code	Condition under which the code is used	Visit (timepoints) where the code is applicable	Applicable for analysis set/endpoint
1070#	Study treatment administered while contraindicated	All	Immunogenicity
1080#	Vaccine temperature deviation	All	Immunogenicity
1090#	Expired vaccine administered	All	Immunogenicity
2010	Protocol violation (inclusion/exclusion criteria) - infant	All	Immunogenicity
2011#	Protocol violation (inclusion/exclusion criteria) - mother	All	Immunogenicity
2040.Vx+*	Administration of any medication forbidden by the protocol - infant	Visit 2-NB/Day 43 post-birth Visit3-NB/Day 121 post-birth Visit4-NB/Day 181 post-birth	Immunogenicity
2040.Vx+*	Device, excluded by the protocol, was administered - infant	Visit 2-NB/Day 43 post-birth Visit3-NB/Day 121 post-birth Visit4-NB/Day 181 post-birth	Immunogenicity
2041#*	Maternal administration of any medication forbidden by the protocol up to Delivery	All	Immunogenicity

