4.2.2. Immunogenicity

4.2.2.1. Analysis of immunogenicity planned in the protocol

The primary analysis for immunogenicity will be based on the PPS for analysis of immunogenicity.

	Primary Immunogenicity Endpoints	Statistical Analysis Methods
Maternal participants	
 • Humoral immune responses at pre-dosing (Day 1) and at delivery: 
 – RSVPreF3 IgG-specific antibody concentrations – Neutralizing antibody titers against RSV-A 	
For each assay, at each timepoint and by study group and age category (<18 years; ≥ 18 years; overall):
 
 • Antibody titers/concentrations will be displayed using reverse cumulative curves. • GMTs/ GMCs will be tabulated with 95% CI and represented graphically. • GMR of antibody titers/concentrations at delivery over pre-dosing will be tabulated with 95% CI. 
Between group evaluation in terms of RSVPreF3 IgG-specific antibody concentrations and neutralizing antibody titers against RSV-A will be performed at delivery using an ANCOVA model on the logarithm₁₀ transformation of the concentrations/titers, and including the pre-dosing logarithm₁₀ transformation of the concentrations/titers, the study intervention, gestational age at the time of study intervention administration (<28^{0/7}; ≥ 28^{0/7} weeks), and the interval between dosing and delivery as covariates if needed.

Cord blood/placental transfer	
Ratio between cord blood* and maternal RSVPreF3 IgG-specific antibody concentrations at delivery.
 
*or infant blood sample collected within 72 hours after birth (if no cord blood sample can be obtained).
	
 • Geometric mean of placental transfer ratio will be tabulated with 95% CI by study group. • Percentage of infants with placental transfer ratio ≥ 1 will be tabulated with exact 95 % CI by study group.

	Primary Immunogenicity Endpoints	Statistical Analysis Methods

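### The infant exclusion code for immunoglobulin and blood products does not cover the substitute birth sample, and the maternal cut-off at delivery can be read two ways

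*SAP*

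**What the plan says.** Both documents allow an infant blood sample within 72 hours of birth to replace missing cord blood, for the birth antibody levels and for the numerator of the transfer ratio. Both are primary immunogenicity endpoints (SAP 4.2.2.1). For the ratio, the SAP plans a geometric mean with 95% CI and adds: "Percentage of infants with placental transfer ratio ≥ 1 will be tabulated with exact 95 % CI by study group".

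For infants, Protocol 9.3.1.1.2 lists RSV-specific immunoglobulin at any time in the study. It also lists immunoglobulins or blood and plasma derivatives given up to Day 43, 121 or 181, according to sub-cohort. Protocol 9.3.1 leaves the complete list of criteria to the SAP. There, Table 8 has code 2040.Vx+, "Administration of any medication forbidden by the protocol - infant", applicable at Visits 2-NB, 3-NB and 4-NB.

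For mothers, Protocol 9.3.1.1.1 eliminates for the products of Section 5.2.1.2 "if administered up to delivery (Visit 3"). That visit has a window of "1 day before to 3 days after delivery" (Protocol Table 3), which the SAP repeats as its per-protocol check: "For PPS at Delivery, check the interval from delivery to delivery BS = 1 day before to 3 days after delivery" (Table 7, code 2090). Code 2041 in Table 8, which carries maternal medication over to the infant, stops at delivery.

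**The concern.** Antibody in a product given to a newborn before a substitute birth sample would be counted as antibody transferred across the placenta. The per-protocol set should remove such a result, and the code written for that purpose does not reach it. After Amendment 1 the code lists only visits that are no longer sampled, so for new infant serology it has no effect.

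On the maternal side, two readers could classify the same woman differently if she received a blood product after birth and before a day 1 to 3 draw. Tables 7 and 8 require case-by-case review by the clinical lead before these codes are assigned, and the study is now unblinded. An exclusion rule that leaves room for choice should therefore be settled before database lock.

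**Working it through.** **1. Infant codes by visit (SAP Table 8)**

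| Code | Visit 1-NB/Birth | Visits 2-NB to 4-NB |
|---|---|---|
| 2040.Vx+ (medication, device) | not listed | listed |
| 1040.Vx+; infant 2050, 2060, 2070.Vx+ | not listed | listed |
| 2090, 2100, 2120, 2130.Vx | listed | listed |

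Table 8 thus treats Visit 1-NB as a sample needing its own checks, but not for medication. The footnote defines Vx+ as elimination from a given visit onwards, so a code that starts at Visit 2-NB cannot remove an earlier birth result.

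*Worked case.* No cord blood; plasma given at 24 hours; infant sampled at 48 hours. Under Protocol 9.3.1.1.2 the product precedes Day 43, 121 and 181, so there is a ground for elimination in any sub-cohort. In SAP Table 8 the sampling interval is within 0 to 72 hours, so 2090 is not triggered, and 2040 does not apply. Only 2120 could apply, and it needs an obvious abnormality or error. The result stays in the birth per-protocol set.

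**2. Maternal rule**

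*Worked case.* Blood product on day 1 after delivery; maternal sample on day 2. If the protocol phrase means the birth, the woman stays in; if it means Visit 3, held on day 2, she can be eliminated. Table 7 code 2040.Vx+ lists Visit 3/Delivery without saying which.

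**3. Size**

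*The plan's own figure.* The only planning figure that rests on the delivery sample is the precision of the fold increase: n = 226, log10 SD 0.4. Half-width = t(0.975, 225) × 0.4 × √2 / √226 = 0.0742, against 0.074 in the plan. A 9-fold increase gives (7.59, 10.68), against (7.6, 10.7). It reproduces, but says nothing about the gap. It gives a scale only: 10^0.074 ≈ 1.19.

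*Infant part (assumed inputs).* If a fraction f of birth results is shifted by a factor s, the geometric mean is multiplied by s^f.
- f = 0.01: 0.996 (s = 0.7) to 1.002 (s = 1.25)
- f = 0.05: 0.982 (s = 0.7) to 1.011 (s = 1.25)

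*Maternal dilution (assumed inputs).* If a fraction f of maternal samples is diluted by d and cord blood is unaffected, the geometric mean ratio is multiplied by (1−d)^(−f).
- d = 10%: 1.011 (f = 0.10), 1.027 (f = 0.25), 1.111 (f = 1)
- f = 0.25, d from 5% to 30%: 1.013 to 1.093

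Share with ratio ≥1 = Φ(log10 GM / SD), with an assumed true GM of 1.2 and log10 SD of 0.15:
- undiluted: Φ(0.0792/0.15) = 0.701
- diluted 10%, GM 1.2/0.9 = 1.333: Φ(0.1249/0.15) = 0.798

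This shift from 70% to 80% applies to affected pairs only. Over d = 5% to 15% and SD = 0.12 to 0.20 the rise is 4 to 15 points in those pairs. With 10% to 25% of pairs affected at d = 10%, the overall rise is 0.10 × 9.7 to 0.25 × 9.7, or about 1 to 2.4 points. At the planned n = 226 the 95% half-width around 70% is 1.96 × √(0.7 × 0.3/226) ≈ 6 points.

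**The case against.** The strongest reply is that the protocol already covers the transfused infant: every infant has a sub-cohort, and a product given on day 1 precedes all three cut-off dates. That is right for the protocol. But its list says only that such products may lead to elimination, and the operative SAP row omits the visit. The gap is therefore one of implementation, and small.

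Other safeguards also stand. Cord blood is the default specimen, and willingness to provide it is an inclusion criterion. Births less than 4 weeks after dosing leave the infant per-protocol set. Cord and infant-drawn samples are evaluated separately if cord blood is missing in 20% or more of a group and the data permit.

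A reader might infer four stronger things that the documents do not support.
- *Maternal blood products around delivery escape the rules.* Products given before birth are covered. For those given afterwards the text is ambiguous, because Visit 3 itself extends to day 3.
- *A maternal transfusion would go unrecorded.* The exemption in Protocol 6.8.1 is for "Standard of care medications/products administered routinely during labor/delivery", with anesthetics and analgesics as examples. Treatment of a haemorrhage is not routine, and Protocol 6.8.3 requires recording of products that bear on evaluability or treat an SAE or AESI.
- *No check on dilution remains.* No elimination code addresses intravenous fluids, and hematocrit collection ends with Amendment 1. But samples already taken can still be used, and the stated purpose was "changes over time in antibody titers / concentrations that may be related to volumetric changes during pregnancy", not peripartum fluids. Sampling before delivery is allowed, including when the line is placed for a cesarean.
- *The vaccine-placebo comparison is biased.* Windows and codes are the same in both groups.

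**Conclusion.** The point holds in a limited form. As written, SAP Table 8 keeps in the birth per-protocol set an infant who received immunoglobulin, blood or plasma before a substitute birth sample, contrary to the grounds that the protocol names. This follows from the text and needs no assumption. The maternal cut-off is ambiguous rather than missing.

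The numerical effect is probably small. The documents give no frequency of missing cord blood, neonatal transfusion, late maternal draws or fluid volume, and no SD for the transfer ratio. Every size above therefore rests on assumed inputs, including that dilution persists to days 1 to 3. The direction is fixed only for maternal dilution with cord blood unaffected, which raises the ratio; donor plasma could move it either way. The 70% to 80% shift is an illustration for affected pairs and should not be read as the expected bias of the endpoint. The within-group transfer outputs are the ones exposed.

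**What to change.** 1. **SAP Table 8, infant code 2040.Vx+.** Add Visit 1-NB/Birth, limited to results from an infant-drawn sample when immunoglobulin, blood or plasma was given before the draw. The limit matters because cord-blood results also sit under this visit and cannot be affected by what the infant receives later. Review at the same time whether 2050 to 2070 need the same entry.
2. **Protocol 9.3.1.1.1 and SAP Table 7, code 2040.Vx+.** State that, for the maternal delivery result and the transfer ratio, the rule runs to the Visit 3 blood draw. Keep the Rho(D) exemption of Protocol 5.2.1.2. Code 2041 can still stop at delivery for the infant's own antibody level.
3. **SAP 4.2.2.1.** As a supportive sensitivity table, repeat the geometric mean ratio and the percentage ≥1 for cord-blood pairs whose maternal sample was drawn before or on the day of delivery. Note beneath it that the split is by calendar day, so a same-day sample may still follow labor fluids or a transfusion.

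*Cost.* Wording changes before database lock and one repeated table. Code 2090 already needs the sampling dates, and Protocol 6.8.3 already requires the relevant products to be recorded, so nothing new is collected. A few participants leave the per-protocol set, and the subset has a wider confidence interval.

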3.2.4. Elimination from solicited safety set

Code 1030 (Study vaccine not administered at all), code 800 (fraudulent data) and code 900 (invalid informed consent) and code 1160 (no post-vaccination solicited safety data) will be used for identifying participants eliminated from the solicited safety set.

4. STATISTICAL ANALYSES

4.1. General Considerations

Unless otherwise specified, reactogenicity analysis will be performed on Solicited Safety Set for maternal participants, and other safety analyses will be performed on Exposed Sets for both maternal and infant participants.

In general, Immunogenicity analysis will be performed on the Per Protocol set. If, in any study group and at any timepoint, the percentage of exposed participants with immunogenicity results excluded from the Per Protocol set is 5% or more, a second analysis based on the Full Analysis Set will be performed to complement the Per Protocol analysis for primary and secondary immunogenicity analysis.

4.1.1. General Methodology

Participants who prematurely withdrew from study will not be replaced.

Unless otherwise specified, continuous data will be summarized using descriptive statistics: n, mean, standard deviation (SD), median, minimum and maximum. Categorical data will be summarized as the number and percentage of participants in each category.

95% confidence interval (CI) for proportion will be based on exact Clopper-Pearson confidence interval [[Clopper, 1934](#)].

95% CI for group difference in proportion will be based on Miettinen and Nurminen confidence interval [[Miettinen, 1985](#)].

95% CI for GMT(C) will be based on a back transformation of student confidence interval for the mean of log-transformation.

95% CI for GMT(C) ratio between groups will be based on a back transformation of confidence interval for the mean difference on log-transformation.

For a given participant and given immunogenicity measurement, missing or non-evaluable measurements will neither be imputed nor be replaced, and therefore will not be included in immunogenicity analysis.

For between group statistical modelling analysis, participants having a result at both the baseline and the considered timepoint will be included in the analysis.

